#### **6.10.1.2 Adverse Event Outcome**

An AE should be followed until the Investigator has determined and provided the final outcome. The outcome should be classified according to the following categories:

- Recovered/resolved: Resolution of an AE with no residual signs or symptoms
- Recovered/resolved with sequelae: Resolution of an AE with residual signs or symptoms
- Not recovered/not resolved (continuing): Either incomplete improvement or no improvement of an AE, such that it remains ongoing
- Fatal: Outcome of AE is death. “Fatal” should be used when death is at least possibly related to the AE
- Unknown: Outcome of an AE is not known (e.g., subject lost to follow-up)

#### **6.10.1.3 Serious Adverse Events**

A serious adverse event is any adverse event that:

- Results in death
- Is life-threatening (the term “life-threatening” here refers to an event in which the participant was at risk of death at the time of the event; it does not refer to an event which hypothetically might cause death if it were more severe)
- Requires inpatient hospitalization or prolongation of existing hospitalization
- Results in persistent or significant disability/incapacity
- Is a congenital anomaly/birth defect
- Would in the opinion of the Investigator jeopardize the participant
- May require medical or surgical intervention to prevent one of the outcomes listed above

#### **6.10.1.4 SAE Reporting Procedure**

Serious adverse events will be collected over the same time period as stated above for AEs. All SAEs must be reported regardless of the relationship to the drug. The initial report should include at least the following information:

- Subject's study ID number
- Protocol number
- Description of the event
- Criterion for categorizing the AE as serious
- Preliminary assignment of causality to study drug

Any new information should be provided as it becomes available. Copies of discharge summaries, consultant reports, autopsy reports, and any other relevant documents may also be requested.

[figure not shown]
Appropriate remedial measure should be taken by the Investigator using his/her best medical judgment to treat the SAE. These measures and the subject's response to these measures should be recorded. All SAEs, regardless of relationship to study drug, will be followed by the Investigator until satisfactory resolution or the investigator deems the SAE to be chronic or stable. Clinical, laboratory, and diagnostic measures should be employed by the Investigator as needed to adequately determine the etiology of the event.

[figure not shown]
The Investigator will be responsible for reporting all SAEs to the Institutional Review Board (IRB)/Ethics Committee (EC). The Sponsor will be responsible for reporting to the regulatory authorities.

Serious adverse events must be reported to the Sponsor within 24 hours of coming to the Investigator's attention. Any serious adverse event that occurs any time after the participant has signed the informed consent form for the study, up to the participant's final study visit, inclusive, is to be reported to Product Safety within 24 hours following when the event was first recognized, discovered, or reported, regardless of severity or relationship to the study product. If unable to enter the SAE information in the EDC (e.g., internet connection is down), the report may be reported by telephone to the Medical Monitor directly [REDACTED]

Serious adverse events must be followed up by the Investigator until resolution or stabilization.

## 7 Study Procedures

## 7.2 Chronological Description of Study Activities

This section describes the schedule of activities per assessment time point. Details of each procedure may be found in [Section 6](#).

[figure not shown]
The timing of all activities for a specific participant are counted in minutes, hours or days relative to the receipt of the study product on minute, hour, Day 0. Unless otherwise noted, the maximal time tolerances on task execution is noted in the Schedules in [Sections 7.1](#) and [7.1.1](#). Priority will be for the PK and PD assessments to be as close to the target time as possible. Deviation from this time window is not considered sufficient to disqualify the participant from per protocol analysis.

The sequence of activities within each visit as described below is not fixed, but may be modified to optimize clinic workflow.

### 7.2.1 Screening

[figure not shown]
Prior to screening for the protocol, the potential participant must be screened for SARS-CoV-2 per investigational site procedures.

1. Informed consent including a signed IRB-approved informed consent form must be obtained before any other study procedures involving the participant are undertaken. The nature of the risks involved and the tasks the participant will do will be explained.
2. Throughout the screening process as outlined below, preliminary assessments of eligibility are performed whenever new information is available and further screening abandoned, if the participant is no longer eligible.
3. The participant's medical history including current conditions will be obtained. For females of current reproductive potential, the history will include current or plans of pregnancy, and for males of current reproductive potential, plans of conceiving or donating sperm during the course of or within 3 months of completing this study.
4. The participant's complete use of concomitant medications including vitamins, herbal supplements and illicit substances will be obtained ([Section 6.2.3](#)).
5. A physical exam including temperature, vital signs, weight and height will be performed ([Sections 6.3.1, 6.5, and 6.6](#)).
6. An ECG will be obtained ([Section 6.7](#)).

[figure not shown]

[figure not shown]
9. The next visit for the check in to the Inpatient Period will be scheduled when all the screening data are anticipated to be available. If the site's procedures for mitigating risk of contagious diseases, including SARS-CoV-2, require additional screening and visits prior to the check-in day -1, these are scheduled at the site's discretion.

### **7.2.2 Day -1, Check-in for Inpatient Period**

[figure not shown]

[figure not shown]
### **7.2.3 Day 0 of Inpatient Period, before and including Injection**

[figure not shown]

#### **7.2.4 Day 0, the First Hour after Injection**

[figure not shown]

[figure not shown]

#### **7.2.5 Day 0 from 1 Hour after Injection**

[figure not shown]

### **7.2.6 Days 1 through 3 of the Inpatient Period**

[figure not shown]

#### **7.2.7 Outpatient Follow-up**

### **7.2.8 Early Termination from Study**

In case of early termination from the study, the last visit to the CRU will include the same assessment as the Day 28 visit plus a careful assessment of the reason for the early termination.

## 7.3 Data Monitoring Board and Dose Escalations

### 7.3.1 Data Monitoring Board

A DMB will be formed to monitor safety and dose cohort choices and provide recommendations to the Sponsor for implementation in the study. The DMB will minimally include an independent Safety Monitor, the Medical Monitor, the Investigator(s), and an independent statistician as voting members, as well as a non-voting coordinator. Operational details will be described in a Safety Plan.

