##### 3.1.3 Staggering of Participants after Dose Escalation (Sentinel Participants)

For the first cohort, one participant will be dosed initially. A review of safety data, including Se-Ca and adverse events (AEs) for the first 72 hours post-dose will be conducted by the Investigator and Medical Monitor. If there are no safety concerns, a second participant will be dosed and the same safety review will be conducted to review data up to 72-hrs post-dose. If there are no safety concerns, the last two participants in the cohort will be dosed.

For subsequent cohorts, this staggering requirement only applies to cohorts for doses higher than previously experienced in the study.

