#### **3.3.5 Blinding**

The primary outcome is safety and tolerability. The assessment relies partly on adverse events evaluations that are prone to reporting bias and can be effectively mitigated with the double-blind design.

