## 5.4 Blinding

### 5.4.1 Treatment blinding

Two Unblinded pharmacy staff members including at least one pharmacist trained to prepare sterile injectables will prepare the doses. The pharmacy staff can have no other role in the study. The doses will be administered by qualified staff trained to administer subcutaneous injections.

With the exception of the DMB members, all other parties remain blinded to the treatment results, until periodic reviews are performed by the DMB.

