### 5.4.2 Endpoint blinding

For safety reasons, no outcomes are blinded.

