- Possible: A “possible” relationship suggests that the association of the AE with the investigational study product is unknown; however, the AE is not reasonably supported by other conditions.
- Probable: A “probable” relationship suggests that a reasonable temporal association of the AE with study product functionality exists and, in the Investigator’s clinical judgment, it is likely that a causal relationship exists between the study product’s functionality and the AE, and other conditions (concurrent illness, progression or expression of disease state or concomitant medication reactions) do not appear to explain the AE.

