### 8.3 Data Analysis

AEs will be presented in listings and Treatment Emergent Adverse Events (TEAEs) will be summarized. Individual results of laboratory tests (hematology, chemistry, and urinalysis) will be listed and change from baseline will be summarized using shift tables. Individual results of vital signs will be listed and observed values and changes from baseline will be summarized.

Individual results of quantitative ECG parameters from the 12-lead safety ECGs will be listed and observed values and changes from baseline will be summarized and analyzed consistent with the ICH E14 (3).

All summaries will be performed by placebo and each EXT608 dose level. Placebo data will be pooled across cohorts. Physical exam findings will be presented in data listings.

Concentrations of EXT608 will be summarized by dose over each scheduled sampling time using descriptive statistics. Individual plasma concentration data versus time will be presented in a data listing. PK parameters will be summarized by dose using descriptive

statistics. Dose proportionality will be assessed graphically and using a power model. PD will be presented in listings and summarized by dose and time point.

Detection of ADA and NAbs will be presented in listings and summarized by dose and time point.

No formal hypothesis testing will be conducted as part of this study.

DMB data packages will be based on the FAS for safety and PP for PK/PD.

Further details are described in the Statistical Analysis Plan.

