## EXTBIO EXT608-101 Statistical Analysis Plan, V2, 2023-JULY-04

- The decision should be documented
- For a blinded trial, the decision should be made before unblinding

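### Protocol 5.4.1 and 7.3.1 take the AE-rating Investigator and the Medical Monitor out of the blind, while SAP 3.5 and Protocol 5.5, 5.4.3 and 10.2 imply that they stay blinded; the plan must say who sees treatment and when

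*Protocol*

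**What the plan says.** **Text that opens the blind**

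- Protocol 7.3.1, on membership: "The DMB will minimally include an independent Safety Monitor, the Medical Monitor, the Investigator(s), and an independent statistician as voting members".
- Protocol 5.4.1, on who is blinded and until when: "With the exception of the DMB members, all other parties remain blinded to the treatment results, until periodic reviews are performed by the DMB".
- Protocol 7.3.2 places the review after the cohort's last participant has completed Day 7 and evaluable data exist. AEs are a primary endpoint from Day 0 to Day 28 (2.1).
- Protocol 8.3, on what the board receives: "DMB data packages will be based on the FAS for safety and PP for PK/PD". Protocol 5.4.2 adds: "For safety reasons, no outcomes are blinded".

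**What these members do with AEs**

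- The sentinel review of safety data "for the first 72 hours post-dose will be conducted by the Investigator and Medical Monitor" (Protocol 3.1.3).
- Causality rests with the Investigator. The definition of a probable relationship turns on the Investigator's "clinical judgment, it is likely that a causal relationship exists between the study product" and the event (6.10.1.1).

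**Text that keeps the blind**

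- SAP 3.5: the interim summaries made for the safety review after each cohort are blinded.
- Protocol 5.5: only the unblinded pharmacist, or an equivalent, knows the code. SAP 2.1.2 also admits an unblinded monitoring person.
- Protocol 5.4.3: the Investigator and Medical Monitor have a code break for a medical emergency.
- Protocol 10.2: treatment-revealing data may be added once clean file has been declared.
- SAP 3.2.4: the medical monitor and statistician decide major violations near the end of the trial, and "For a blinded trial, the decision should be made before unblinding".

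SAP 1.4 records no modification from the protocol's statistical section.

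**The concern.** Protocol 3.3.5 justifies the double-blind design because safety assessment relies on "adverse events evaluations that are prone to reporting bias and can be effectively mitigated with the double-blind design". The protection works only if the people who judge AEs do not know the arm. Sections 5.4.1 and 7.3.1 together place the Investigator among those excepted from the blind, with the Medical Monitor alongside.

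The incidence, nature and severity of AEs to Day 28 are the first primary endpoint. A rater who knows the arm can call an event related on EXT608 and dismiss the same event on placebo, or the reverse. Relatedness also feeds the escalation tree in 3.1.5, which counts Grade 3 events suspected to be related to study drug.

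Removing arm labels may not be enough. Cohorts of 4 are randomized 3:1 in blocks of 4, so identifying the one placebo participant reveals all four assignments. If the DMB package shows PK by participant, PK can do that.

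**Working it through.** The plan states no figure for this point, so there is none to reproduce. The check has two parts: set the passages side by side, then compute how much of the AE window each reading exposes.

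**1. Three readings of the same documents**

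- *Reading A, 5.4.1 literal.* DMB members are excepted from the start. The Investigator and Medical Monitor are DMB members, so they may see treatment throughout: 28/28 days = 100%.
- *Reading B, the blind ends at the cohort's DMB review.* This follows the last clause of the 5.4.1 sentence. The exposed share depends on when the DMB meets.
- *Reading C, SAP 3.5 and Protocol 5.5 govern.* Summaries are blinded and only pharmacy holds the code: 0% is exposed through the DMB.

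A and C cannot both be true. An emergency code break (5.4.3) would be unnecessary for people who already see treatment. A medical monitor unblinded at the reviews could not decide violations before unblinding at the end of the trial (SAP 3.2.4).

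**2. Reading B in numbers**

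Inputs:

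- AE window of 28 days (Protocol 2.1).
- Review no earlier than the last participant's Day 7 (7.3.2).
- Stagger of participant 1, then 2, then 3 and 4 together, with 72 hours of data between steps (3.1.3). The earliest dosing days are therefore d = 0, 3, 6, 6.
- Lag L from the last Day 7 to the DMB meeting. The documents do not give it; I assume 0 to 14 days.

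Formulas: review day R = (last dosing day) + 7 + L. Days left for participant i = 28 − (R − dᵢ). Cohort share = (sum of days left)/(4 × 28).

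Staggered cohort, L = 0: R = 13, so the days left are 28 − 13 = 15, 28 − 10 = 18, 28 − 7 = 21 and 21. The sum is 75, and 75/112 = 67.0%. Each day of lag removes 4 participant-days, so the share is (75 − 4L)/112.

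Unstaggered cohort (a repeat at a dose already given): 4 × 21 = 84 at L = 0, so the share is (84 − 4L)/112.

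| Lag L (days) | Staggered | Unstaggered |
|---|---|---|
| 0 | 75/112 = 67.0% | 84/112 = 75.0% |
| 2 | 67/112 = 59.8% | 76/112 = 67.9% |
| 4.75 | 56/112 = 50.0% | 65/112 = 58.0% |
| 7 | 47/112 = 42.0% | 56/112 = 50.0% |
| 14 | 19/112 = 17.0% | 28/112 = 25.0% |

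For the first staggered participant the share is (15 − L)/28, which falls below half once L exceeds 1 day. A longer stagger than the minimum lowers the staggered figures further.

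**3. What Reading B leaves untouched**

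The injection-site endpoint runs from Day 0 to Day 7, so it is complete before the review. The seven-day data that feed the escalation decision also precede that cohort's review. On Reading B the exposure falls on AEs rated after the review; only Reading A reaches the escalation inputs.

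**The case against.** The strongest reply is that the plan does not unblind the raters at all. SAP 3.5 says the interim summaries are blinded, Protocol 5.5 confines the code to pharmacy, 5.4.3 presupposes a blinded Investigator and Medical Monitor, and 10.2 holds back treatment-revealing data. Section 5.4.1 speaks of treatment results, which need not mean the code. DMB operations are left to a Safety Plan that is not among these documents and may already separate open from closed sessions. The study is descriptive, with no formal hypothesis testing.

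Much of this stands, and it rules out several stronger inferences a reader might draw:

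- *That the plan chooses to have AEs rated unblinded.* Too much text points the other way; the documents support a contradiction.
- *That most of the 28-day window is exposed.* This is certain only under Reading A. Under Reading B it depends on an unstated lag, and under Reading C the share is zero.
- *That the Medical Monitor rates causality.* The documents show a reviewing role; the causality judgment is the Investigator's.
- *That per-protocol exclusions are made unblinded.* SAP 3.2.4 requires the opposite; the difficulty is that 5.4.1 may make that requirement impossible to meet. Safety analyses use the FAS in any case.
- *That 5.4.2 unblinds treatment.* It says outcomes are not masked, which is a different matter from assignment.

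What does not stand is that the contrary text cures the problem. SAP 1.4 claims no departure from the protocol's statistical section, so the SAP does not present itself as overriding 5.4.1. A Safety Plan should not have to contradict the protocol to preserve the blind. Descriptive AE rates are still open to rating bias.

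**Conclusion.** The point holds as an inconsistency on who is unblinded and when. Protocol 5.4.1 with 7.3.1, followed as written, lets the person who judges AE causality, and the Medical Monitor who shares the early safety reviews, see treatment while the primary AE window is open. Other sections of both documents say or presuppose that they cannot.

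The exposed share runs from 0% to 100% according to which passage governs. The intermediate figures rest on the minimum stagger, the assumed lag and the blind ending at the DMB review. They measure calendar time, not events; AEs may cluster soon after dosing, and the documents give no event timing. The inconsistency does not depend on any of these percentages. It should be settled before any further DMB review, because a blind cannot be restored once raters have seen assignments.

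**What to change.** - **Protocol 5.4.1:** limit the exception from the blind to the independent Safety Monitor and the independent statistician. Replace the closing clause, which ends everyone else's blind at the DMB reviews, with one that runs until database lock. Keep the emergency code break in 5.4.3.
- **Protocol 7.3.1:** the Investigator(s) and Medical Monitor keep their votes but receive packages without arm labels and without participant-level PK. Arm-level and PK data go only to the two independent members.
- **SAP 3.5 and 2.1.2:** state the same arrangement, naming who holds the code and which summaries are blinded to whom.

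The cost is protocol, SAP and Safety Plan wording plus a data-routing instruction. No new members are needed. The tree in 3.1.5 uses AE grades and serum calcium, so withholding participant-level PK removes none of its inputs. No dose or escalation rule changes.

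The downsides are that the arm-level view rests on two existing DMB members, and the other voters decide with less information than 5.4.1 would now allow them. Serum calcium and the other safety laboratory results stay open for safety, so some functional unblinding remains.

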### 7.3.2 Dose Escalations

When the last participant of a cohort has completed Day 7 and evaluable data are available, statistics will provide a data summary of the cohort data for the DMB. The DMB will meet and decide further actions as described in the Safety Plan.

## 8 Statistical Methods

### 8.1 Sample size

The sample size is not determined for inferential testing purposes. The sample size of 4 participants per cohort (3 active: 1 placebo) is considered sufficient for evaluation of safety, tolerability, and PD of EXT608 prior to making a decision about dose escalation as Se-Ca is very tightly regulated and determination of effect based on simulations can therefore reliably be made with the small sample.

### 8.2 Analysis populations

Two participant populations will be defined. The Safety of Full Analysis Set population (FAS) will be defined as all participants who are randomized. The Per-Protocol (PP) population will be participants for whom evaluable data to and including Day 7 is available and with no major protocol violations.

### 8.3 Data Analysis

AEs will be presented in listings and Treatment Emergent Adverse Events (TEAEs) will be summarized. Individual results of laboratory tests (hematology, chemistry, and urinalysis) will be listed and change from baseline will be summarized using shift tables. Individual results of vital signs will be listed and observed values and changes from baseline will be summarized.

Individual results of quantitative ECG parameters from the 12-lead safety ECGs will be listed and observed values and changes from baseline will be summarized and analyzed consistent with the ICH E14 (3).

All summaries will be performed by placebo and each EXT608 dose level. Placebo data will be pooled across cohorts. Physical exam findings will be presented in data listings.

Concentrations of EXT608 will be summarized by dose over each scheduled sampling time using descriptive statistics. Individual plasma concentration data versus time will be presented in a data listing. PK parameters will be summarized by dose using descriptive

statistics. Dose proportionality will be assessed graphically and using a power model. PD will be presented in listings and summarized by dose and time point.

Detection of ADA and NAbs will be presented in listings and summarized by dose and time point.

No formal hypothesis testing will be conducted as part of this study.

DMB data packages will be based on the FAS for safety and PP for PK/PD.

Further details are described in the Statistical Analysis Plan.

## **9 Direct Access to Source Data/Documents**

Extend Biosciences, Inc. or agents thereof, the reviewing IRB/EC, and health authorities from the US or other countries will have access to source documents at the investigational site for monitoring, auditing or inspection purposes.

## **10 Quality Control and Quality Assurance**

### **10.1 Monitoring**

The study will be monitored by qualified site monitors approved by the Sponsor.

Monitoring will be done via on-site visits by the site monitor, who will review the eCRFs and source documents, and via remote review of eCRF entries. The site monitor will make sure that the investigation is conducted according to protocol design, GCP, and regulatory requirements.

Alternatively, due to the ongoing SARS-CoV-2 pandemic, all monitoring may be remote using a combination of source documents uploaded to the EDC and other tools for viewing site documents, e.g., for signed ICFs, for SDV. Further details will be described in a Clinical Monitoring Plan.

